A catheter will be inserted into a radial artery using ultrasound guidance, lidocaine local anesthetic and aseptic technique to acquire samples for blood gas analysis and continuously monitor the arterial blood pressure (Edwards Lifesciences Truwave). A catheter will also be inserted into a peripheral vein using aseptic technique to facilitate the infusion of fentanyl. Oxygen will be continuously delivered using a soft tight-fitting face mask connected to an anesthesia circuit (FIO2-1.0) with a side-port for continuous sampling of inspired/expired gas (sampling line to BIOPAC CO2100C gas analyzer). Respiratory rate and airflow will be continuously measured using a commercial reference pneumotachometer attached to the inlet of the face mask (BIOPAC TSD117A). All cardiovascular, respiratory, and sound monitoring will be continuously recorded through a BIOPAC MP150 data acquisition system connected to a desktop computer. Pictures may be taken after instrumentation.

Monitored study subjects will be instructed to rest comfortably in the supine position and refrain from talking. A standard IV dose of Ondansetron will be administered to minimize the risk for nausea/emesis. A standard IV dose of glycopyrrolate may be administered to minimize the risk for bradycardia. Vital signs and respiratory data will be recorded

during a 1-hour baseline period while sampling arterial blood every 15 minutes to measure pH, PaCO₂, PaO₂, HCO₃, SaO₂ and lactate concentrations (Epoc blood analysis system, Siemens, München, Germany).

After an initial bolus of 1.0 mcg/kg, a stepwise continuous intravenous infusion of fentanyl will be started at time zero (Figure 2). The infusion will start at 1.5 mcg/kg/hr and will be increased by 1.5 mcg/kg every 30 minutes. The infusion will be continued for a maximum duration of 3 hours (final infusion rate 9.0 mcg/kg/h). In a 30-year old 70 kg man, the proposed stepped infusion is projected to cause a gradual increase in fentanyl plasma concentration up to a maximum concentration of 5.8 ng/mL (Figure 3). Respiratory depression typically occurs anywhere in the 2.0 – 6.0 ng/mL fentanyl plasma concentration range (7, 8) while loss of consciousness occurs around 34 ± 7 ng/mL (7).

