Vital sign monitor data, CO₂ waveform data, reference pneumotach data, and tracheal sound data will be continuously recorded throughout the infusion protocol. Arterial blood gases will be measured every 10 minutes, or immediately after the decision is made to stop the infusion protocol. The fentanyl infusion will be discontinued prior to the end of the 3 hour protocol if: (1) the PaCO₂ exceeds 60 mm Hg in two consecutive blood gas measurements (primary end-point), (2) the subject requires positive pressure bag/mask assisted ventilation by the anesthesiologist, or (3) the SaO₂ falls below 90% on supplemental oxygen (FIO₂=1.0).

The primary endpoint of the study will be the onset of moderate hypoventilation, defined as two consecutive arterial PaCO₂ measurement ≥ 60 mmHg. This level of opioid induced hypoventilation is clinically significant because based upon the alveolar gas equation and the Henderson-Hasselbalch equation- breathing room air (FIO₂ 21%) at sea level (barometric pressure 760 mm Hg) (9), a PaCO₂ of 60 mm Hg will decrease the PaO₂ from 159 mm Hg to 75 mm Hg to produce an arterial partial pressure of oxygen (PaO₂) ~75 mmHg. The respiratory acidosis will cause the hemoglobin oxygen dissociation curve to shift to the right and downward leading to an arterial hemoglobin oxygen saturation of ~88% SaO₂.

Respiratory and vital sign data will continue to be collected for another 2 hours after discontinuation of the fentanyl infusion. Arterial blood will be sampled every 15 minutes for pH and blood gas analysis. The total volume of blood sampled will be approximately ~45 ml over a 6 hour study period (25 samples x 1.5 ml/sample = 45 ml). The narcotic antagonist Naloxone and other emergency medications will be immediately available as needed to ensure safety. After the 2 hour post infusion measurements, subjects will eat a meal and be observed for another hour or more to confirm adequate minute ventilation.

After completion of the experiment, study subjects will be given oral and written instructions similar to patients undergoing an outpatient surgical center procedure under general anesthesia. Each subject will receive a phone call around 9 pm that evening and a phone call 5-7 days later to confirm no study related adverse events.

Summary of Subject Monitoring:

- 1) Radial artery catheter to monitor and record the arterial blood pressure waveform.
- 2) Heart rate & rhythm will be monitored and recorded by an electrocardiogram.

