The aim of the present protocol is to induce mild to moderate respiratory depression up to the described endpoint of two consecutive PaCO₂ measurements ≥ 60 mmHg. The fentanyl infusion will be stopped if: (1) the partial pressure of carbon dioxide exceeds 60 mm Hg in two consecutive blood gas measurements (primary end-point), (2) the subject requires positive pressure bag/mask assisted ventilation by the anesthesiologist, or (3) the hemoglobin oxygen saturation falls below 90% on supplemental oxygen (FIO₂ = 1.0), (4) one blood gas of PaCO₂ > 70 mmHg, and/or (5) two consecutive blood gas measurements with pH < 7.20 .

Potential Benefits of Proposed Research to Human Subjects & Others- Risk/Benefit Ratio:

The risks of a slow intravenous infusion of fentanyl to induce hypoventilation managed by an experienced anesthesiologist are low. We do not anticipate any benefits of participating in this study to the human volunteer subjects. The benefit of developing an algorithm capable of detecting and preventing severe hypoventilation, hypoxemia and death due to an opioid overdose is significant. The clinical investigative team has a variety of systems and procedures in place to maximize subject safety. In the United States opioid related overdose is currently a leading cause of death in people aged <50 years (1). An accurate tool to alert first responders or family and friends in the case of an impending overdose would have significant societal impact and would potentially prevent a significant number of deaths by allowing for the timely administration of naloxone. In the hospital setting there is also a need for a continuous monitor of minute ventilation (MV = RR x TV) to improve the safety of opioid analgesia (5).

H. Data and Safety Monitoring Plan

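### Section D's list of infusion stops omits two safety limits that Section G requires: a single PaCO₂ above 70 mmHg and two consecutive pH values below 7.20

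*Protocol*

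**What the plan says.** Section D of the Protocol (Human Clinical Study - Visit # 2) gives the reasons for ending the infusion before three hours. The list opens "The fentanyl infusion will be discontinued prior to the end of the 3 hour protocol if: (1) the PaCO₂ exceeds 60 mm Hg" on two consecutive gases. Its second item is the need for bag/mask ventilation, and its last is "or (3) the SaO₂ falls below 90% on supplemental oxygen (FIO₂=1.0"). The list closes there and does not refer to any other section.

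Section G (Specific Procedures and Risks, following the fentanyl infusion item) gives a list that opens "The fentanyl infusion will be stopped if: (1) the partial pressure of carbon dioxide exceeds 60 mm Hg" on two consecutive gases. It repeats the ventilation and saturation stops and continues: "4) one blood gas of PaCO₂ > 70 mmHg, and/or (5) two consecutive blood gas measurements with pH < 7.20".

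Both are current text. In both sections the first stop is labelled as the primary endpoint and requires PaCO₂ above 60. Section D defines that endpoint as moderate hypoventilation, "defined as two consecutive arterial PaCO₂ measurement ≥ 60 mmHg", and Section G describes it the same way: "up to the described endpoint of two consecutive PaCO₂ measurements ≥ 60 mmHg".

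During the infusion, "Arterial blood gases will be measured every 10 minutes, or immediately after the decision is made to stop the infusion protocol". On dosing, "The infusion will start at 1.5 mcg/kg/hr and will be increased by 1.5 mcg/kg every 30 minutes", with a final rate of 9.0 mcg/kg/h.

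**The concern.** The stops are safety limits for healthy volunteers who are deliberately made to hypoventilate and are not expected to benefit. Section D is where the infusion schedule and gas schedule are set, and its list reads as complete. It contains no limit that a single PaCO₂ value can trigger, however high that value is. Someone running the visit from that list could continue fentanyl after one reading above 70 mmHg, which Section G says must end the infusion.

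It would also be unclear what counts as a deviation: continuing after that reading complies with Section D's list and breaches Section G's. A smaller point in the same sentences is that the stop named after the primary endpoint uses a strict inequality, while the endpoint itself includes 60.

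**Working it through.** **1. The two lists side by side**

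| Stop | Section D | Section G |
|---|---|---|
| PaCO₂ > 60 mmHg, two consecutive gases | yes | yes |
| Bag/mask ventilation needed | yes | yes |
| Saturation < 90% on FIO₂ 1.0 | yes | yes |
| One PaCO₂ > 70 mmHg | no | yes |
| Two consecutive pH < 7.20 | no | yes |

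The first three match in substance. Section D has 3 of 5.

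**2. When the 70 mmHg stop makes a difference.** The lists diverge when a gas above 70 follows a gas of 60 or below, with saturation at least 90% and no assisted ventilation. As an illustration, take 58 then 72 mmHg.

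- Section D: only one reading exceeds 60, so its PaCO₂ stop is not met.
- Section G: 72 > 70, so the infusion stops.

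**3. Would the saturation stop cover the gap?** Inputs are FIO₂ 1.0 and barometric pressure 760 mmHg (both in Section D) and an assumed water vapour pressure of 47 mmHg. On pure oxygen, alveolar PO₂ = (760 − 47) − PaCO₂ = 713 − PaCO₂. At 70 mmHg this is 643; at 72 it is 641. A saturation below 90% would not be expected. Section D's own discussion of anticipated problems also describes the hypoxemia risk on supplemental oxygen as minimal.

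**4. Extra drug over one gas interval.** Dose = rate × 10/60.

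| Rate (mcg/kg/h) | 1.5 | 3.0 | 4.5 | 6.0 | 7.5 | 9.0 |
|---|---|---|---|---|---|---|
| Extra dose (mcg/kg) | 0.25 | 0.50 | 0.75 | 1.00 | 1.25 | 1.50 |

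For scale, the starting bolus is 1.0 mcg/kg. If the next gas is still above 60, Section D's first stop then applies and the excess is one interval. If it has fallen to 60 or below, Section D's list lets the infusion continue.

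**5. When the pH stop makes a difference.** pH = 6.1 + log₁₀[HCO₃ / (0.03 × PaCO₂)], with assumed pK 6.1 and solubility 0.03. At pH 7.20, HCO₃ = 0.03 × 10^1.1 × PaCO₂ = 0.3777 × PaCO₂. At PaCO₂ 60 this gives 22.7 mEq/L. A pH below 7.20 with PaCO₂ no higher than 60 therefore needs HCO₃ below about 22.7, so the pH stop adds to Section D only in that range.

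In the 58/72 example, the pH pairs are:

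| HCO₃ (mEq/L) | pH at 58 | pH at 72 |
|---|---|---|
| 22 | 7.202 | 7.108 |
| 24 | 7.240 | 7.146 |
| 26 | 7.274 | 7.181 |

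Only the second gas is below 7.20 in each case, so in that example the 70 mmHg limit alone triggers Section G's stop. Below an HCO₃ of 0.3777 × 58 = 21.9 both gases would be under 7.20 and Section G would stop on pH as well. Section D would still not stop.

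**6. The 60 mmHg symbol.** Two readings of exactly 60 meet the endpoint but not the stop labelled with its name. The same holds for one reading of 60 paired with a higher one. The two definitions agree everywhere else.

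**The case against.** The strongest reply is that no stop is missing from the Protocol. Section G is binding, Section D does not call its list exhaustive, and both can be followed at once. On that reading this is a repetition that was not kept in step, with nothing wrong in the design itself. That description is fair, but it does not make the Section D list complete.

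The divergence is also narrow. PaCO₂ must go from 60 or below to above 70 between gases ten minutes apart, during an infusion the Protocol describes as slow. One experienced anesthesiologist manages every subject, airflow and expired CO₂ are recorded continuously, naloxone is at hand, and an independent medical monitor reviews deviations. These safeguards lower the likely harm, and the 58/72 pair is only an illustration. They do not tell staff which list governs.

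Figure 2 (Fentanyl Infusion Protocol) is not shown and may carry all five stops. If it does, Section D has the information but its text still lags.

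Finally, the pH calculations are not needed to show the omission. That is correct: they only show that the pH stop is the lesser of the two gaps. The threshold symbol is likewise a minor, separate point that adds little weight.

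**Conclusion.** The concern holds. Section D's text lists three of the five stops that Section G requires. The important omission is the single-gas limit of 70 mmHg, the only PaCO₂ limit in either list that one reading can trigger. Where the lists diverge, Section D alone allows at least one further 10-minute interval of fentanyl, 0.25 to 1.5 mcg/kg depending on the infusion step, unless another stop applies. The pH omission matters only when HCO₃ is below about 22.7 mEq/L.

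The item count and dose range come directly from the Protocol. The alveolar oxygen and pH figures rest on the standard constants assumed above. The frequency of either situation cannot be estimated from the document. The matter should be corrected because it concerns safety limits in the operative section, although clinical supervision reduces the likely consequence. The mismatch between above 60 and at least 60 is minor.

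**What to change.** Add Section G's fourth and fifth stops (one PaCO₂ above 70 mmHg; two consecutive pH values below 7.20) to the Section D list, so that both sections carry the same five. If Figure 2 shows stopping criteria, check that it agrees. In the same edit, choose either ≥ 60 or > 60 and use it in both sections for the stop labelled as the primary endpoint and for the endpoint definition.

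The cost is a wording correction. Blood gases including pH and PaCO₂ are already measured, so no procedure, sample, visit or data field is added.

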This is a pilot study and we therefore do not have prior data to conduct a power analysis. Because sound and physiological data will be collected continuously, even a relatively small number of subjects will provide a significant data set for algorithm development. If we assume a respiratory rate of 12 breaths per minute then: 12 breaths per min x 60 mins per hr = 720 breaths per hr; 720 breaths x 6 hr study time per patient = 4,320 breaths per patient; 4,320 breaths per patient x 6 subjects = 25,920 breaths for all 6 subjects. Previous studies on analysis of tracheal sound to track ventilation have used a similar n, with sometimes shorter protocols (2).

The performance of the developed prediction algorithm will be evaluated by looking at the mean absolute error in predicted PaCO₂ vs. the actual PaCO₂ and by comparing predicted time to hypoventilation during the fentanyl ramp vs. the observed time to hypoventilation. We plan to perform analysis on data from an initial 6 study subjects, then study up to 20 subjects to produce a more robust machine learning algorithm that detects/predicts the onset of mild and moderate hypoventilation.

F. Gender/Minority/Pediatric Inclusion for Research

Minorities will be eligible to participate in the research. Children (age < 18 years) will be excluded from participation. We aim to recruit robustly healthy young subjects for this initial proof of concept effort, because we anticipate that they will tolerate this protocol very well. We anticipate studying populations that are more varied if the proposed proof of concept study is successful.

G. Human Subjects

Inclusion criteria will be:

1. Healthy women/men between 18 and 40 years of age.
2. Negative history of drug or alcohol abuse.
3. Negative history of cigarette smoking in previous 6 months.
4. Negative history of active cardiac, vascular, pulmonary, renal, hepatic, nervous, metabolic or immune disease.
5. BMI < 30

Exclusion criteria will be:

1. Age < 18 years and > 40 years.
2. Pregnant or planning to become pregnant.
3. Positive history drug or alcohol abuse.
4. Positive drug screen for opioids, benzodiazepines, hypnotics.
5. Positive Drug Abuse Screening Test result (score of 6 or greater).
6. BMI > 30
7. History of sleep apnea.
8. History of cigarette smoking in previous 6 months.
9. History of difficult airway during anesthesia management.
10. History of allergy or skin sensitivity to tape, silicone, fentanyl, chlorhexidine.

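### Does the blood-gas line, where 25 samples of 1.5 ml are said to make 45 ml, leave the sampling schedule in doubt?

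*Protocol*

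**What the plan says.** All the relevant text is in section D, under Visit # 2, apart from the evaluation plan in section E.

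- Baseline: vital signs and respiratory data are recorded "during a 1-hour baseline period while sampling arterial blood every 15 minutes".
- Infusion length: "The infusion will be continued for a maximum duration of 3 hours".
- Infusion sampling: "Arterial blood gases will be measured every 10 minutes, or immediately after the decision is made to stop the infusion protocol".
- Recovery length: "Respiratory and vital sign data will continue to be collected for another 2 hours after discontinuation of the fentanyl infusion".
- Recovery sampling: "Arterial blood will be sampled every 15 minutes for pH and blood gas analysis".
- Blood volume: approximately 45 ml, "over a 6 hour study period (25 samples x 1.5 ml/sample = 45 ml".

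The primary endpoint is moderate hypoventilation, shown by two consecutive arterial gases at the PaCO₂ threshold. Section E judges the algorithm by its mean absolute error against measured PaCO₂ and by "comparing predicted time to hypoventilation during the fentanyl ramp vs. the observed time to hypoventilation".

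**The concern.** The blood-volume line is printed as an equation, and the equation is false. The word for approximately in front of the total does not excuse it, because the printed total is 20% above its own product (45/37.5 = 1.2).

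The count also disagrees with the schedule. If 12 draws go to baseline and recovery, 25 leaves 13 for the infusion, where a 10-minute interval over three hours needs 18. Moreover, 25 is the number obtained by sampling every 15 minutes for six hours with an opening draw (360/15 + 1). A reader could suspect that the count belongs to a different plan from the interval text.

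If the infusion interval really were in doubt, the matter would be more than editorial. The spacing of the gases limits how closely the onset of hypoventilation can be timed, and it sets how many reference PaCO₂ values per subject enter the mean absolute error. The volume is also a burden figure for healthy volunteers who are not expected to benefit, so it ought to be right.

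**Working it through.** **Inputs**, all from section D: baseline 60 min at 15-minute intervals; infusion at most 180 min at 10-minute intervals; recovery 120 min at 15-minute intervals; 1.5 ml per sample; stated count 25; stated total 45 ml. The three phases sum to 60 + 180 + 120 = 360 min, so the six-hour figure describes the full-length session.

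**The plan's own line.** Count x volume = 25 x 1.5 = 37.5 ml. The printed 45 ml is not reproduced. Working back from the total, 45/1.5 = 30 samples. Keeping the count instead, 45/25 = 1.8 ml per sample, which is not the stated volume.

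**Draws required by the schedule** (phase length / interval):

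| Phase | Calculation | Draws |
|---|---|---|
| Baseline | 60/15 | 4 |
| Infusion | 180/10 | 18 |
| Recovery | 120/15 | 8 |
| Total | 4 + 18 + 8 | 30 |

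30 x 1.5 = 45.0 ml, exactly the stated total. With one opening draw the count is 31 and the volume 46.5 ml, still about 45 ml. Under either convention 25 is short, by 5 or by 6.

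**Does 25 point to a 15-minute infusion interval?** The counting convention has to be held fixed:

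| Convention | Written schedule | 15 min throughout |
|---|---|---|
| No opening draw | 30 | 360/15 = 24 |
| With opening draw | 31 | 24 + 1 = 25 |

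The match to 25 needs an opening draw, whereas the match of the schedule to 45 ml needs none. Setting 30 against 25 therefore mixes the two conventions.

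Nor is the 15-minute reading the only way to reach 25. Under the written intervals, an infusion stopped at 130 min gives 4 + 13 + 8 = 25 draws. That session lasts 60 + 130 + 120 = 310 min, or 5 h 10 min, so it does not rescue a line that speaks of six hours. It does show that a count alone cannot identify an interval.

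**Is there a competing statement?** The 15-minute interval is stated for baseline and for recovery. For the infusion the only stated interval is 10 minutes.

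**The case for a change.** The best case for acting is that the line is wrong on its face, can be checked in seconds, and is not explained by early stopping or by a different volume per sample. Staff who planned supplies or sampling from the count could under-sample the ramp, and a protocol should not contain a false equation. Correcting it would cost one line.

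Much of this stands. The product is wrong and 25 draws do not cover the six-hour schedule.

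The harm to the study does not follow. The instructions that staff carry out are the intervals; the parenthesis only supports a volume estimate. Any effect on onset timing or on the mean absolute error requires staff to disregard the stated interval in favour of a count that the protocol allocates to no phase. Even the figure of 13 infusion draws assumes that all 12 baseline and recovery draws are taken in full. Consequences worked out from a 15-minute infusion interval rest on an inference from the count, and nothing in the text supports it.

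**Conclusion.** The slip is real and clerical. The count of 25 disagrees with everything around it, while the intervals, the volume per sample and the total agree at 30 draws and 45 ml. The discrepancy is 5 draws (6 with an opening draw) and 45 − 37.5 = 7.5 ml. Because the printed total matches the schedule, the 7.5 ml is not a demonstrated error in the burden figure.

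Correcting the count would alter no endpoint, no analysis, no sample size and no conclusion, so no change to the plan is called for. The count can be brought into line with the intervals and the total whenever the text is next edited.

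This rests on two assumptions: that the team samples by the written intervals, and that the volume line describes a session with the full three-hour infusion, as its reference to six hours indicates. Three hours is a maximum, so subjects who stop early will have fewer draws. That is a feature of the design and does not bear on the printed line. No view is taken here on what the sampling interval ought to be.

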We hypothesize that advanced analysis of tracheal sound can be used to predict hypoventilation due to opioid overdose.

The specific aim of this proof of concept study is to collect tracheal sound data in 20 healthy subjects undergoing an incremental infusion of fentanyl to induce mild to moderate hypoventilation (also called permissive hypercapnia). Study subjects will receive supplemental oxygen to prevent hypoxemia. The tracheal sound data will be refined using advanced signal processing techniques and machine learning to assess whether it is possible to detect and predict the onset of hypoventilation.

The long-term objective of this project is to develop a real-time monitoring system based on tracheal sound that can be used to detect changes in minute ventilation and alarm before significant hypoventilation occurs due to an overdose of anesthetics and/or analgesics.

B. Background and Significance

RTM Vital Signs, LLC is collaborating with Thomas Jefferson University to develop a non-invasive Tracheal Sound Sensor that continuously monitors and analyzes sounds from the trachea to determine upper airway patency and the adequacy of an ambulatory person's respiratory rate (RR) and tidal volume (TV) to maintain a sufficient minute ventilation (RR X TV).

Over the last decades various mathematical methods have been developed to estimate respiratory rate and respiratory flow from tracheal sounds (2). Airflow sounds are known to occur at a frequency of 200-2000 Hz while snoring sounds occur in the 0-200 Hz band (2). There is a near-linear relationship between airflow in the trachea and respiratory sounds - increasing flow increases the amplitude of sounds. Additionally, different transformations can be applied continuously on recorded tracheal sound to extract specific information.

Previous studies have looked at the average power, envelop, spectral power, and entropy of sound signals. One of the most robust models to estimate respiratory flow from tracheal sound uses the entropy of tracheal sounds (a measure

[figure not shown]

Figure 1. Actual tracheal airflow (solid line) measured with a reference pneumotachometer and estimated airflow using a microphone over the sternal notch and entropy model (dashed line). Figure modified from Yadollahi and Moussavi (2).

of sound complexity) to determine tracheal airflow during inhalation and exhalation (Figure 1) (2, 4).

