A pilot human clinical study that utilizes fentanyl to induce mild and moderate hypoventilation will be conducted in 20 healthy adults to collect the data necessary to develop a diagnostic algorithm that functions as a risk-index score that continuously predicts the onset of mild and moderate hypoventilation using signal processing and machine learning methods.

Informed Consent/Screen- Visit # 1:

Subjects will arrive at the Department of Anesthesiology's research office. [name] will review the informed consent document and the inclusion/exclusion criteria. Subjects will complete a Drug Abuse Screening Test (DAST)(6) to determine their risk for substance abuse (Attachment 1). They will also provide a urine sample to perform a drug screen toxicology analysis. For women, we will also provide urine pregnancy testing. [name] will also review the informed consent document, answer any of the subject's questions and obtain a signed consent form. Each subject will receive a copy of the consent form. [name] will then perform a detailed history and physical exam and review the subject's vital sign data. [name] will then schedule the clinical study visit # 2.

Human Clinical Study - Visit # 2:

Study subjects will be instructed to refrain from eating after 11 pm (NPO) the day prior to the study and to arrive at Thomas Jefferson University Hospital around 7 am on the morning of study visit # 2. A urine drug screen toxicology test will be repeated on all study subjects. For female subjects, we will also conduct urine pregnancy testing.

Subjects will be studied in a hospital clinical environment containing an anesthesia machine, vital sign monitors and routine emergency equipment, medications and supplies. All study subjects will be managed by [name], D.O. an experienced board-certified anesthesiologist with extensive experience in the respiratory effects of an IV infusion of fentanyl. Subjects will be continuously monitored using standard anesthesia vital sign monitors (ECG/upper arm cuff BP/pulse oximeter, Datex Ohmeda) and a BIS sedation monitor (Covidien) according to American Society of Anesthesiology standards. A contact microphone (BIOPAC TSD108) will be adhered to the skin over the trachea (above the sternal notch) with double-sided tape and a Tegaderm bandage. An accelerometer will be adhered to the skin close to the microphone.

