Study Subject Recruitment & consent:

Twenty healthy volunteers will be recruited from the general population around Thomas Jefferson University using an advertising flier (Attachment 2). Potential subjects will contact the Anesthesiology

research nurse coordinator [name], R.N. to review the inclusion/exclusion criteria and schedule visit # 1 (Attachment 3, phone script). Subjects will arrive at the Department of Anesthesiology's research office. [name] will review the informed consent document and the inclusion/exclusion criteria. Subjects will complete a Drug Abuse Screening Test (DAST) (6) to determine their risk for substance abuse (Attachment 1). They will also provide a urine sample to perform a drug toxicology analysis. In female potential subjects, we will also perform a urine pregnancy test. [name] will also review the informed consent document with subjects during visit #1, answer any of the subject's questions and obtain a signed and witnessed consent form. Each subject will receive a copy of the consent form. [name] will then perform a detailed history and physical exam and review the subject's vital sign data. [name] will then schedule the clinical study visit # 2 in 2 to 6 weeks.

General Approach to Minimize Risk:

We plan to study only young and healthy subjects with a good airway, at very low risk for an anesthetic complication. Clinical trials have demonstrated the safety of managing hospitalized patients with mild to moderate permissive hypercapnia, as long as hypoxemia is avoided (12). Subjects will be studied in a hospital clinical environment containing an anesthesia machine, vital sign monitors and routine emergency equipment, medication and supplies. [name] will use TJUH standard of care operating procedures and other well-accepted safety strategies to minimize risk. Supplemental oxygen will be continuously delivered via face mask to significantly minimize the risk of hypoxemia during fentanyl induced hypoventilation.

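### Does an analysis at 6 subjects followed by a ceiling of 20 conflict with the fixed total of 20 given elsewhere?

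*Protocol*

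**What the plan says.** Three sections of the protocol give a single number. Section A (Specific Aims) sets out to "collect tracheal sound data in 20 healthy subjects undergoing an incremental infusion of fentanyl". Section D (Research Design and Methods) says the pilot "will be conducted in 20 healthy adults to collect the data necessary to develop a diagnostic algorithm". The recruitment text in Section G (Human Subjects) says "Twenty healthy volunteers will be recruited from the general population".

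Section E (Statistical Methods) opens with "This is a pilot study and we therefore do not have prior data to conduct a power analysis". It then supports the size with a breath count worked for six people: "4,320 breaths per patient x 6 subjects = 25,920 breaths for all 6 subjects". Performance is to be judged on the average absolute PaCO₂ error and on predicted against observed time to hypoventilation. The section closes with "We plan to perform analysis on data from an initial 6 study subjects, then study up to 20 subjects", and the rest of that sentence gives the reason for going on: a sturdier algorithm.

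**The concern.** A ceiling is not a target. Taken alone, the last sentence of Section E names no minimum and does not say what role the analysis at 6 plays. The only quantitative rationale in that section is worked for 6, so a reader could take the other 14 subjects (20 − 6 = 14, or 70% of 20) as optional.

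Two things would then be at stake:

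- **Precision.** What the study shows about a new person depends on the number of people, not the number of breaths, because breaths within one person are correlated. Ending well short of 20 would leave the performance estimate much less certain.
- **Selective stopping.** If enrolment ended because the error in the first 6 looked good, the reported error would be too favourable on average, and the protocol would give no criterion against which to judge that decision.

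**Working it through.** **1. The plan's own figure.** Inputs from Section E: 12 breaths per minute, 6 hours per subject, 6 subjects.

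- 12 × 60 = 720 breaths per hour
- 720 × 6 = 4,320 per subject
- 4,320 × 6 = 25,920, which matches the stated figure

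At 20 subjects the same formula gives 4,320 × 20 = 86,400, or 20/6 = 3.3 times as many. The count at 6 describes the data available for the first analysis. It does not set a total.

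**2. The possible readings of Section E.**

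| Reading | Total | Fits Sections A, D and G? |
|---|---|---|
| First batch of 6, then on to 20 | 20 | Yes |
| Stop anywhere from 6 (or 7) to 20 | below 20 possible | No, whenever below 20 |
| 6, then 20 more | 26 | No |

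Only the first reading satisfies all four sections. It also fits the sentence itself, which plans the step past 6 and gives it a purpose. No sentence ties that step to the result at 6. The only authority to halt the study as a whole that the protocol describes is the medical monitor's in Section H, and that concerns safety.

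**3. What the total is worth.** The 95% half-width for a mean of per-subject errors, in between-subject SDs and assuming approximate normality, is t(0.975, n − 1)/√n:

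- n = 6: 1.05
- n = 10: 0.72
- n = 20: 0.47

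The total matters, by a factor of 1.05/0.47 = 2.2 between the extremes. But the protocol promises no precision at any n, and the reading that satisfies every section delivers the value at 20.

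**4. The selective-stopping worry, given a number.** This needs a rule that the protocol does not contain. Assume that enrolment stops at 6 when the mean error of the first 6 is no worse than its true mean and otherwise runs to 20, with normal per-subject errors and an algorithm that does not change.

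- Stopped studies (half of them): −√(2/π)/√6 = −0.33 SD
- Continued studies: (6/20) × 0.326 = +0.10 SD
- Over all studies: 0.5 × (−0.326) + 0.5 × 0.098 = −0.11 SD

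Moving the threshold from +0.5 to −0.5 SD gives a bias of 0.09 to 0.70 SD in stopped studies and 0.05 to 0.11 SD overall. At the middle threshold, the overall bias is 0.114/0.468 = 24% of the half-width at 20, and the bias in stopped studies is 0.326/1.049 = 31% of the half-width at 6. The fixed-algorithm assumption also departs from Section E, where the added subjects serve to improve the algorithm, so the model at 20 is not the model at 6.

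**The case for a change.** The strongest case for a change is that the number of volunteers given fentanyl and an arterial catheter belongs in the protocol, not in an analysis plan. A protocol that states 20 in three places and a ceiling in a fourth leaves the reader to supply the reconciling interpretation. The breath count supports 6 and not 20, and the only reason for going further is a general wish for robustness. One sentence would remove the doubt.

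Part of this stands. Section E is looser than the other sections, and it does not say outright that the analysis at 6 has no bearing on the total. If the study did end early, the reason would not be on record in the protocol.

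The rest does not carry. A short study would not pass unnoticed, because Sections A, D and G would each show it as falling below plan. Those sections need not mention the analysis at 6, since aims and recruitment text do not normally list analyses. Asking for a decision criterion presumes a decision that the protocol never describes. How an early development analysis is run and used is commonly left to the statistical analysis plan, which is not shown here.

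**Conclusion.** This is a small looseness of wording with an obvious reconciliation: 6 is a first development batch, and 20 is both the planned total and the cap. A team that follows the protocol as it naturally reads studies 20 subjects and obtains the same result with or without different wording. No figure is wrong, and no rule in the document would produce a wrong answer. There is no power, alpha or stated precision for the ambiguity to damage. Rewording would record an intention already given in three sections. It would be a reasonable tidy-up if the document were being amended anyway, but not a reason to amend it.

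The conclusion rests on taking the three unqualified statements of 20 as the plan and on the absence of any performance-based stopping. If the sponsor did intend the result at 6 to decide the total, the bias would depend on a rule not yet written. Under the rules assumed above it would be at most about 0.11 SD averaged over all studies, though larger (0.09 to 0.70 SD) in those that stopped.
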